## **6. OBJECTIVES**

### **6.1. Study Objectives**

#### **6.1.1. Primary Objective**

The primary objective of this study is to evaluate the effectiveness of A-101 45% compared to Vehicle when applied twice weekly to common warts.

#### **6.1.2. Secondary Objectives**

The secondary objectives of this study include:

- Duration of response to A-101 45% compared to Vehicle.
- Onset of action of A-101 45% compared to Vehicle.
- Safety of A-101 45%.

## **7. STUDY DESIGN**

This is a phase 3, multicenter, randomized, vehicle controlled, double blind parallel group study designed to evaluate the efficacy and safety of A-101 45% compared to Vehicle in subjects with common warts.

During the study, the investigator will identify at least 1 and up to 6 common warts to be treated twice a week for up to 8 weeks (maximum of 16 treatment applications)

Subjects will be required to complete a total of 13 study visits. The protocol defined study visits are:

- Visit 1 (Day -13 to 0) screening
- Visit 2 (Day 1)\* randomization; study medication treatment
- Visit 3 (Day 8)\* study medication treatment
- Visit 4 (Day 15)\* study medication treatment
- Visit 5 (Day 22)\* study medication treatment
- Visit 6 (Day 29)\* study medication treatment
- Visit 7 (Day 36)\* study medication treatment
- Visit 8 (Day 43)\* study medication treatment
- Visit 9 (Day 50)\* study medication treatment
- Visit 10 (Day 60) follow up evaluations, no identified Wart retreatment
- Visit 11 (Day 78) follow up evaluations, no identified Wart retreatment
- Visit 12 (Day 106) follow up evaluations, no identified Wart retreatment
- Visit 13 (Day 137) follow up evaluations, no identified Wart retreatment; end of study

\*The second weekly application will be applied by the subject/parent/legal guardian at home (Day 4, 11, 18, 25, 32, 39, 46, and 53).

Refer to [Table 2](#) for a complete list of protocol required study assessments.

### **7.1. Number of Subjects and Study Centers**

Approximately 500 subjects will be randomized to one of two treatment arms at approximately 25 investigational centers in the US. Of the 500 subjects randomized, approximately 100 subjects will be between 1 and 17 years of age.

### **7.2. Duration of Study**

The anticipated time for study enrollment is approximately 3 months. The duration of study participation is anticipated to be a maximum of 157 days per subject. Subjects will have a total of 13 study visits. The maximum anticipated duration for the study is approximately 10 months.

## 8. STUDY ENTRY CRITERIA

### 8.1. Inclusion Criteria

Subjects must meet all the following criteria to be considered for participation in this study.

1. Subject or legal guardian is able to comprehend and is willing to sign an informed consent/assent for participation in this study.
2. Male or female  $\geq 1$  year old.
3. Subject has a clinical diagnosis of common warts (*verruca vulgaris*).
4. Subject has at least 1 and up to 6 clearly identifiable common warts located on the trunk or extremities that meet the requirements as defined below:
  - a. Have a longest axis that is  $\geq 3$  and  $\leq 8$  mm and have a thickness of  $\leq 3$ mm
  - b. Be a discrete lesion, i.e. each wart meeting the entry criteria is clearly separated from other warts.
  - c. Be present for at least 4 weeks
  - d. Not be covered with hair which, in the investigator's opinion, would interfere with the study medication treatment or the study evaluations
  - e. Not be in an intertriginous fold
  - f. Periungual, subungual, genital, anal, mosaic, plantar, flat and filiform warts are excluded from treatment and evaluation. If a subject has these types of warts, but also has warts that meet the inclusion criteria, the subject will NOT be excluded from the study.
5. Each common wart identified for treatment must have a PWA  $\geq 2$ .
6. Subject's chemistry and complete blood count results are within normal limits. If any of the laboratory values are outside normal range, the treating investigator must assess the value(s) as NOT clinically significant and document this in the subject's medical chart in order for the subject to be eligible for randomization.
7. Subject is in good general health and free of any known disease state or physical condition which, in the investigator's opinion, might impair the evaluation of the identified common warts or which exposes the subject to an unacceptable risk by study participation.
8. Subject is willing and able to follow all study instructions and to attend all study visits.
9. Subject must be the only individual in a household participating in the study.

### 8.2. Exclusion Criteria

Subjects are excluded from this study if any of the following criteria is met:

1. Subject has clinically atypical warts.
2. Subject is immunocompromised (*e.g.*, due to chemotherapy, systemic steroids, genetic immunodeficiency, transplant status, etc.).
3. Subject has a history of Human Immunodeficiency Virus (HIV) infection.
4. Subject has had any Human Papilloma Virus (HPV) vaccine within 6 months prior to Visit 1.
5. Subject has used any of the following intralesional therapies within the specified period prior to Visit 2:
  - Immunotherapy (*e.g.*, *Candida* antigen, mumps antigen, *Trichophyton* antigen); 8 weeks
  - Anti-metabolite therapy (*e.g.*, bleomycin, 5-fluorouracil); 8 weeks

6. Subject has used any of the following systemic therapies within the specified period prior to Visit 2:
  - Immunomodulatory/immunosuppressant therapy (*e.g.*, etanercept, alefacept, infliximab); 16 weeks
  - Glucocortico-steroids (inhaled and intra-nasal steroids are permitted); 28 days
7. Subject has used any of the following topical therapies within the specified period prior to Visit 2 on, or in the proximity to any of the common warts identified for treatment, that in the investigator's opinion interferes with the study medication treatment or the study assessments:
  - LASER, light or other energy-based therapy (*e.g.*, intense pulsed light [IPL], photodynamic therapy [PDT]); 180 days
  - Immunotherapy (*e.g.*, imiquimod, squaric acid dibutyl ester [SADBE], etc.) 12 weeks
  - Liquid nitrogen, electrodesiccation, curettage; 60 days
  - Hydrogen peroxide; 90 days
  - Antimetabolite therapy (*e.g.*, 5-fluorouracil); 8 weeks
  - Retinoids; 90 days
  - Over-the-counter (OTC) wart therapies and cantharidin; 28 days
8. Subject currently has or has had any of the following within the specified period prior to Visit 1 on or in the proximity to any of the common warts identified for treatment that, in the investigator's opinion, interferes with the study medication treatment or the study assessments:
  - Cutaneous malignancy; 180 days
  - Sunburn; currently
  - Pre-malignancy (*e.g.*, actinic keratosis); currently
9. Subject has a history of sensitivity to any of the ingredients in the study medications.
10. Subject has any current skin or systemic disease (*e.g.*, psoriasis, atopic dermatitis, eczema, sun damage), or condition (*e.g.*, sunburn, excessive hair, open wounds) that, in the opinion of the investigator, might put the subject at undue risk by study participation or interfere with the study conduct or evaluations.
11. Participation in another therapeutic investigational drug/device trial in which administration of an investigational treatment occurred with 30 days prior to Visit 1.
12. Subject has an active malignancy.
13. Subject is viewed by the Principal Investigator as not being able to complete the study.

### **8.3. Removal of Subjects from Study Therapy**

A subject may be removed from the study therapy for a variety of reasons, including:

- Unacceptable adverse event
- Subject unwilling or refusal to continue with the protocol defined study visits and/or consent withdrawal for study participation
- Change in compliance with an inclusion/exclusion criteria
- Use of a prohibited medication (through Visit 13)
- General or specific changes in the subject's condition that render the subject unacceptable for further treatment in this study in the judgement of the investigator.

Aclaris Therapeutics, Inc.

Protocol Number: A-101-WART-301

Amendment 3: Version 5 14 February 2019

If a subject is to be withdrawn from the study, the Aclaris Therapeutics, Inc. CRA or designee must be informed within 24 hours of the decision to remove the subject from the study.

The study may be discontinued at the discretion of Aclaris Therapeutics, Inc. Some examples of reasons for discontinuation are the occurrence of the following:

- Increased frequency, severity or duration of known AEs
- Medical, regulatory or ethical reasons affecting the continued performance of the study
- Difficulties in the recruitment of subjects

#### **8.4. Withdrawal Procedures**

If a subject withdraws from the study prior to Visit 13, the reason for and the date of withdrawal from the study must be recorded on the eCRF. If the reason for withdrawal is an adverse event or a clinically significant abnormal laboratory test result, monitoring of the subject will continue until the event has resolved or stabilized, until the patient is referred to the care of a local health care professional, or until a determination of a cause unrelated to the study drug or study procedure is made.

#### **8.5. Subject Replacement**

Subjects that are determined to be screen failures may be rescreened for the study and if determined to be eligible for the study they may be randomized using the same subject identifier. A screen failure is a subject that signs an informed consent form for participation in the study but is determined not to be eligible for the study prior to the subject being randomized to the study.

#### **8.6. Subject Identifier (SI)**

The investigator or designee will assign a unique five-digit subject identifier (SI) to each subject at Visit 1.

The SI format will be NN-NNN where the first 2 digits are the investigational center site number (using leading zeroes, as appropriate). The final 3 digits are the subject number and must be assigned in ascending numerical order, without omitting or repeating any number, starting with 001 at each investigational center. For example, the SI for the second subject that signs an informed consent at site number 04 would be 04-002.

The subject will be identified using the SI in all study documentation for the duration of the study.

Aclaris Therapeutics, Inc.

Protocol Number: A-101-WART-301

Amendment 3: Version 5 14 February 2019

## **9. STUDY PROCEDURES**

The schedule of study activities (including assessments, tests, exams, disease assessments, and study drug administration) beginning with screening and continuing through the end of study are outlined in [Table 2](#) . A written, signed informed consent form (ICF) must be obtained from each subject prior to performing any study related procedure (*e.g.*, vital signs, clinical laboratory sampling, or photography).

Aclaris Therapeutics, Inc.

Protocol Number: A-101-WART-301

Amendment 3: Version 5 14 February 2019

**Table 2: Study Procedures**

Visit	V1 Screening	V2	V3	V4	V5	V6	V7	V8	V9	V10	V11	V12	V13
Treatment Day	-13 to 0	1	8	15	22	29	36	43	50	60	78	106	137
Treatment Window	N/A	N/A	±1 day	+4 days	±7 days	±7 days	+7 days						
Study Procedures													
Informed Consent	▲												
Inclusion Criteria/Exclusion Criteria	▲	▲ 											
Subject Identifier	▲ 												
Medical history/demographics	▲												
Fitzpatrick Skin Type Assessment	▲ 												
Vital Signs	▲ 								▲				▲
Prior Medications/Therapies	▲ 												
Clinical Chemistry and CBC 	▲												▲
Common Wart Identification 	▲												
Physician's Wart Assessment 	▲	▲	▲	▲	▲	▲	▲	▲	▲	▲	▲	▲	▲

Visit	V1 Screening	V2	V3	V4	V5	V6	V7	V8	V9	V10	V11	V12	V13
Treatment Day	-13 to 0	1	8	15	22	29	36	43	50	60	78	106	137
Treatment Window	N/A	N/A	±1 day	±1 day	±1 day	±1 day	±1 day	±1 day	±1 day	+4 days	±7 days	±7 days	+7 days
Common Wart Dimensions 	▲	▲	▲	▲	▲	▲	▲	▲	▲	▲	▲	▲	▲
Standardized Photography 	▲	▲ 		▲		▲			▲	▲	▲	▲	▲
Subject Randomization		▲ 											
Local Skin Reactions		▲ 	▲ 	▲ 	▲ 	▲ 	▲ 	▲ 	▲	▲	▲	▲	▲
Study Medication Application 		▲	▲	▲	▲	▲	▲	▲	▲				
Study Medication Application at Home 			A-101 Study Medication will be applied at home on Days 4, 11, 18, 25, 32, 39, 46, 53. A window of +1 day is allowed.										
Subject Instructions	▲	▲	▲	▲	▲	▲	▲	▲	▲	▲	▲	▲	
Concomitant therapies 		▲	▲	▲	▲	▲	▲	▲	▲	▲	▲	▲	
Adverse Events 		▲	▲	▲	▲	▲	▲	▲	▲	▲	▲		

Subject inclusion/exclusion criteria will be re-assessed prior to randomization during Visit 2.

Investigational sites will assign a unique five-digit subject identifier to each subject at Visit 1. This subject identifier will be used in all study documentation for the duration of the study.

Each subject’s skin must be assessed during Visit 1 using the Fitzpatrick Skin Type Assessment.

Aclaris Therapeutics, Inc.

Protocol Number: A-101-WART-301

Amendment 3: Version 5 14 February 2019

Vital signs [including temperature, pulse, respiratory rate, blood pressure, height and weight (Visit 1 only)] will be measured by a qualified staff member at Visit 1, Visit 9 and Visit 13.

Prior medications/therapies will be collected for a time-period of 14 days prior to Visit 2. Refer to Section 11 for a list of permitted and restricted concomitant medications.

A complete blood count (including hematocrit, hemoglobin, platelet count, red blood cell count and morphology, white blood cell count and differential (absolute and %) including basophils, eosinophils, lymphocytes, monocytes and neutrophils and a clinical chemistry panel including albumin, alkaline phosphatase, alanine aminotransferase (ALT), aspartate aminotransferase (AST), blood urea nitrogen (BUN), bicarbonate, calcium, chloride, creatinine, glucose, lactate dehydrogenase (LDH), phosphorus, potassium, sodium, total bilirubin, total protein, and uric acid.

The treating investigator will identify at least 1 and up to 6 common warts located on the trunk or extremities that meet the inclusion criteria outlined in Section 7.

 The investigator will use the Physician Wart Assessment (PWA) scale to assess each identified common wart. The investigator must assess the identified common warts prior to application of the study medication at Visit 2-Visit 9. In order to be eligible for randomization at Visit 2, each common wart must have a PWA grade  $\geq 2$ .

 The investigator will measure the dimensions (longest axis and thickness of the common wart) at Visit 1 and prior to randomization at Visit 2. In order for the subject to be randomized at Visit 2 the identified common warts must have the specific dimensions outlined in Section 12.1. The investigator will be required to measure the longest axis of each common wart at Visits 2-13.

 At Visits 1, Visit 2, 4, 6, and 9 (prior to study medication application), and Visit 10-13, a qualified investigational center staff member will take a photograph of each identified common wart using the Aclaris supplied camera. All photographs will be sent to a central imaging laboratory.

At a sub-set of investigational sites (up to 3 sites), subjects randomized at these sites will have additional standardized photographs taken of their common warts at the following time-points: V2-10 minutes post application, 1-hour post application and 24 hours post application.

Subjects will be randomized at Visit 2 prior to application of study medication. Investigational study staff will re-confirm subject eligibility prior to randomization.

 The investigator and subject will assess each identified common wart for local skin reactions associated with irritation at Visits 2-13. At Visit 2-Visit 9, the investigator and subject will assess each identified common wart for LSRs prior to the application of the study medication. Refer to Section 13.1 for the complete list of Local Skin Reaction signs and symptoms.

During in-office visits, subjects 18 years of age and older will apply their A-101 study medication in the presence of the treating physician or a member of the investigational study staff that has been trained on the protocol. Subjects ages 1 to 17 will have their A-101 study medication applied by a parent/legal guardian in front of the treating physician or a member of the investigational study staff during in-office visits. If the identified common wart meets the criteria

Aclaris Therapeutics, Inc.

Protocol Number: A-101-WART-301

Amendment 3: Version 5 14 February 2019

for re-treatment as defined in Section 10.6 the lesion will be re-treated at Visits 3-9. Following application of study medication, subjects must NOT wash/submerge the treated wart for at least 6 hours and they must NOT apply any topical products to the treated common warts for at least 6 hours. Parents/legal guardians of children must ensure that the child does not put the treated area in their mouth, or eyes, until completely dry after the application. If the treated area is not completely dry 10 minutes after the application, the area should be blotted dry.

All subjects will receive their second weekly treatment of the A-101 study medication at home on Days 4, 11, 18, 25, 25, 32, 39, 46, 53 as determined by the PWA assessment performed during the in-office visit. Subjects ages 1 to 17 will have their A-101 study medication applied by a parent or legal guardian. All subjects will need to document the application of A-101 study medication in a subject diary. The second weekly treatment will depend on the PWA performed during the in-office visit that week. If the identified common wart meets the criteria for re-treatment during the in-office visit, then the subject/parent/guardian will perform the second weekly treatment at home.

All concomitant therapies including (topical and oral) prescription medications, over the counter medications and natural supplements and non-drug therapies including chiropractic, physical therapy, and energy-based therapy must be documented in the subject CRF. Subjects must not apply any topical products (*e.g.*, moisturizers, sunscreen, etc.) to the identified common wart within 12 hours prior to any study visit.

The reporting period for Serious Adverse Events (SAEs) begins when the subject signs the informed consent and continues through Visit 11. Refer to Section Section 14.1.2 for instructions on the reporting of SAEs. Non-serious clinical adverse events will be collected following the application of the study medication at Visit 2 and through Visit 11. Non-serious adverse events that occur between the time of consent and study medication application will be documented as medical history. All safety reporting (AEs and SAEs) will conclude at Visit 11 (approximately 28 days after last study medication application) except for clinical adverse events related to local skin reactions.

## 10. STUDY TREATMENT

### 10.1. Investigational Study Medication

The study medications for the study are A-101 45%, and matching Vehicle. All study medications are clear, colorless solutions which are indistinguishable in physical appearance.

**Table 3: Study Medication Information**

Study Medication Name	A-101 45%	Vehicle
Manufacturer	James Alexander Corporation, Blairstown NJ	
A-101 concentration (%)	45	0
Pharmaceutical Form	Solution	
Storage Conditions	59°F to 77°F (15°C to 25°C) excessive heat, open flame and combustibles, out of direct sunlight and in a well-ventilated, dry area	
Route	Topical	
Frequency	A-101 Study Medication will be applied twice a week for 8 weeks.	
Duration of Administration	Apply study medication to each identified common wart for approximately 15 seconds. Allow each treated wart to remain undisturbed for approximately 15 seconds. Repeat the application/waiting cycle until the study medication has been applied to each identified common wart up to 3 times.	
Activated Applicators	Activated applicators are stable for 4 hours at room temperature (59°F to 77°F or 15°C to 25°C)	

### 10.2. Subject Randomization

Prior to the start of the study, Aclaris Therapeutics, Inc./designee will generate a randomization list that will be provided to the assigned clinical packaging organization for study medication labeling.

The randomization list will be stored with limited access to designated personnel for study medication labeling.

Aclaris Therapeutics, Inc.

Protocol Number: A-101-WART-301

Amendment 3: Version 5 14 February 2019

Subjects will be randomized to the study in a 1:1 ratio and stratified by investigational study site. Sites will be shipped study medication in blocks of 4. Once a subject is determined to have met all inclusion criteria and does not meet any of the exclusion criteria, the site will pull the next sequential drug kit from their supply and enter the drug kit number into the EDC system.

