- If severe erythema and edema develop, then the treatment cycle should be discontinued for that specific treatment application.
- Absorb any remaining A-101 study medication and dry the common wart and the surrounding skin without wiping or rubbing.

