### 12.4. Subject Instructions

An investigational center staff member will dispense a Subject Instruction Sheet to each subject at Visit 1 (Refer to [Appendix 1](#)).

Throughout the study, the subjects should:

Aclaris Therapeutics, Inc.

Protocol Number: A-101-WART-301

Amendment 3: Version 5 14 February 2019

- Continue their routine cleansing regimen except they should avoid vigorous scrubbing of the identified common warts (*e.g.*, loofah, back brushes, scrubbing straps, abrasive washcloths, sponges and cleansing pads, etc.)
- Continue their routine cosmetics and skin care products
- Avoid exposing the identified common warts to excessive natural or artificial ultraviolet radiation (*e.g.*, sunlight, tanning beds) and use sunscreen on the common warts, if excessive exposure cannot be avoided
- Avoid activities that might irritate the common warts.
- Avoid the use of self-tanning lotions and spray tans near the common warts.
- Bring the subject instruction sheet and subject diary with them to each visit.
- Follow all instructions for the proper application of the A-101 study medication when applying product at home.

On study visit days, the subjects should:

- Wear loose fitting clothing to the visit (Note: clothing that comes in contact with the study medication may be bleached)
- Starting with Visit 2, not apply any topical products to the identified common wart within **12 hours** prior to the visit (Note: routine cleansing products are allowed)
- After the completion of any study visit where a study medication treatment was performed DO NOT:
  - Wash/submerge the treated common wart for at least **6 hours**
  - Apply any topical products to the treated common wart for at least **6 hours**.

**12.5. Parents/legal guardians of children must ensure that the child does not put the treated area in their mouth, or eyes, until completely dry after the application. If the treated area is not completely dry 10 minutes after the application, the area should be blotted dry.****Other Study Supplies**

Aclaris Therapeutics, Inc. will provide:

- An appropriate ruler, or other instrument, for measuring of all common wart dimensions;
- Supplies and instructions for collecting, labeling, shipping and result reporting for the clinical laboratory tests from ACM Laboratories;
- Nitrile examination gloves
- Equipment, supplies and training for taking standardized photographs;

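### Section 10.2 discloses supply in blocks of 4 with sequential kits pulled by the site, so later kits in a block become partly predictable if reactions reveal earlier assignments

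*Protocol*

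**What the plan says.** Four statements in Protocol Section 10.2 fix the allocation mechanism:

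- Before the study starts, the sponsor or its designee "will generate a randomization list that will be provided to the assigned clinical packaging organization for study medication labeling". Access to that list is restricted.
- The ratio and the strata are given as: "Subjects will be randomized to the study in a 1:1 ratio and stratified by investigational study site".
- On supply, the only block size named anywhere is here: "Sites will be shipped study medication in blocks of 4".
- Once eligibility is met, "the site will pull the next sequential drug kit from their supply and enter the drug kit number into the EDC system".

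No other or varying block size is named, and nothing says that block size is withheld from sites. Section 7.1 gives the scale: "Approximately 500 subjects will be randomized to one of two treatment arms at approximately 25 investigational centers in the US".

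On masking, Section 10.1 says: "All study medications are clear, colorless solutions which are indistinguishable in physical appearance". The comparison, however, is 45% hydrogen peroxide against 0% (Table 3), and the protocol foresees effects that staff could see. Section 12.4 warns that "clothing that comes in contact with the study medication may be bleached". Section 10.7 provides: "If severe erythema and edema develop, then the treatment cycle should be discontinued for that specific treatment application". Section 5.2 reports crusting, edema, erythema and scaling after treatment in Phase 2, and describes local reactions as mostly mild and short-lived. Section 14.2.1 has site staff watch each subject for at least 20 minutes after an in-office treatment.

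**The concern.** The protocol restricts access to the randomization list, yet gives sites the parameters that make the list partly predictable. If the randomization block is 4 with two kits of each arm, concealment of the next assignment depends on how well blinding holds for the earlier subjects in that block.

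The investigator who might form such a guess also rechecks eligibility at Visit 2 just before randomization (Table 2, footnotes 1 and 12). Some criteria are matters of judgement: general health (inclusion 7), undue risk or interference with evaluations (exclusion 10), and expected ability to complete the study (exclusion 13). A guess about the next kit could influence whether a subject is randomized, or when. The two arms could then differ at baseline in ways the analysis does not adjust for.

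**Working it through.** The protocol states no predictability figure, so there is none to reproduce.

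**Inputs.** Block of 4 with two kits per arm (inferred from Section 10.2); about 500 subjects at about 25 sites (Section 7.1); enrollment over about 3 months (Section 7.2). The accuracy q with which a site infers an earlier subject's arm is not in the document. It is assumed to range from 0.5 (no information) to 1 (full knowledge).

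**Scale.** 500/25 = 20 subjects per site, and 20/4 = 5 blocks per site.

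**Ceiling, q = 1.** A 2:2 block has 6 equally likely orders, giving 6 × 4 = 24 positions.

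- Best-guess probabilities at positions 1 to 4 are 1/2, 2/3, 2/3 and 1. The mean is (1/2 + 2/3 + 2/3 + 1)/4 = 17/24 = 70.8%.
- The fourth position is always certain (6 of 6). The third is certain when the first two match (2 of 6). Together that is 8/24 = 33.3%, or about 500/3 = 167 subjects.

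**Imperfect inference.** With each earlier assignment read correctly with probability q:

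- position 1: 1/2
- positions 2 and 3: (1 + q)/3 each
- position 4: q² + 2q(1 − q)², the chance that the majority of the three readings points the right way

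| q | positions 2 and 3 | position 4 | mean of four |
|---|---|---|---|
| 0.5 | 50.0% | 50.0% | 50.0% |
| 0.6 | 53.3% | 55.2% | 53.0% |
| 0.7 | 56.7% | 61.6% | 56.2% |
| 0.8 | 60.0% | 70.4% | 60.1% |
| 0.9 | 63.3% | 82.8% | 64.9% |
| 1.0 | 66.7% | 100% | 70.8% |

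For example, at q = 0.8 position 4 is 0.64 + 2 × 0.8 × 0.04 = 0.704, and the mean is (0.5 + 0.6 + 0.6 + 0.704)/4 = 0.601.

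**Timing.** Taking 3 months as 91 days and accrual as even, a site randomizes one subject about every 91/20 = 4.55 days. When the fourth kit of a block is pulled, the first and second subjects started about 13.7 and 9.1 days earlier. Both would normally have reached Visit 3 (Day 8, 7 days after Day 1). The third started about 4.6 days earlier and has been seen only during and after the first in-office application. The cues are therefore available in time, but not equally for every predecessor, which argues against q = 1.

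**Effect of the fix.** Simulation of a best guesser with full knowledge of earlier assignments, who knows the set of block sizes but not their order (20 subjects per site, 4,000 replicates):

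| block sizes | certain | guessed correctly |
|---|---|---|
| 4 only (exact) | 33.3% | 70.8% |
| 4/6 | 5.8% | 68.6% |
| 2/4/6 | 3.8% | 69.5% |
| 4/6/8 | 2.4% | 67.4% |

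**The case against.** Several points on the other side carry weight.

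- A reader might infer that the protocol declares a constant randomization block of 4. It does not. The sentence describes shipment. With site stratification and sequential kits, a randomization block of 4 is the natural reading, but it remains an inference. If the restricted specification uses other sizes, the figures for a fixed block of 4 do not apply.
- A reader might infer that the investigator can choose which and how many warts to identify according to the expected arm. The documents give little support. Warts are identified at Visit 1 (Section 12.1, Table 2), up to about two weeks before the kit is pulled. Laboratory results are reviewed in between (Section 13.3), and other screened subjects may be randomized first. The primary test, and the first secondary test, are also stratified by the baseline number of treated warts (Section 15.3), which blunts any imbalance in count.
- A reader might take 33% and 71% as expected values. They are ceilings that assume every earlier assignment is known. Phase 2 reactions were mostly mild, no rates by arm are given, both arms have the wart rubbed firmly with alcohol before application, and the bleaching remark is a precaution about clothing.
- The remedy is partial. If reactions do unblind, the same investigator's wart rating is exposed whatever the block size. The document is already at Version 5, so removing the sentence cannot undo earlier disclosure.

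These points limit the size and the route of the problem. The disclosure itself, and discretion over eligibility and timing at Visit 2, are untouched by them.

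**Conclusion.** The point stands as a conditional weakness in allocation concealment. It is neither a contradiction nor a wrong figure, and it does not affect the sample size or power. Mean guess accuracy lies between 50% (no leakage) and 70.8% (full leakage), and is about 53% to 65% for q between 0.6 and 0.9. At most about one assignment in three is certain.

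This rests on two assumptions: that the randomization block equals the shipping block of 4, and that reactions reveal treatment to some degree. The document makes the second plausible but does not quantify it. The credible route to bias is the decision whether and when to randomize at Visit 2, rather than wart count. Nothing in the document shows that such selection has occurred. The case for changing the text is that the improvement is cheap.

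**What to change.** In Section 10.2, delete the reference to blocks of 4. State only that allocation is 1:1, stratified by site, with block details held in a restricted randomization specification not available to sites. For kits not yet labelled and shipped, generate the list with randomly varying, undisclosed block sizes. The shipping quantity need not match the randomization block.

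The benefit is mainly the removal of certainty: certain assignments fall from 33% to about 2% to 6%, while average guess accuracy falls only from 71% to about 67% to 70%.

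The cost is a wording change, a regenerated list and labelling for the affected kits, and slightly looser balance within site. The largest imbalance inside an open block is half its size: 2 for a block of 4, 3 for 6, 4 for 8. Whether any kits remain unshipped is not stated; if none do, only the wording change is possible. Neither step protects the wart rating from unblinding.
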